Section of Geriatrics and Gerontology

Department of Medicine and Neurology

Emory University

[contact]

[name] MPH (Co-Investigator, Postdoc Fellow)

Department of Neurology

Emory University

[contact]

[name] (Co-investigator, Neuropsychologist)

Department of Neurology

Emory University

[contact]

[name] (Statistician)

Department of Neurology

Emory University

[contact]

PARTICIPATING STUDY SITES

Wesley Woods Health Center

Emory University Hospital Clinical Research Network

Executive Park Medical Campus

PRÉCIS

Study Title

Effects of Montelukast Therapy on Alzheimer's Disease

Acronym

EMERALD

Objectives

Our *primary objective* is to determine the safety, dose-response and target engagement of the treatment with escalating doses of Montelukast in those with mild cognitive impairment (MCI) or early Alzheimer's disease (AD) dementia.

Our *secondary objectives* are to assess the efficacy and estimate the effect size of up to 1-year treatment of Montelukast on biomarkers of neurodegeneration and cognition in MCI/early AD dementia.

Design and Outcomes

This is a double-blind placebo-controlled randomized clinical trial that compares Montelukast to placebo in individuals with MCI and early AD dementia. Our measures include cognitive function, CSF biomarkers and neuroimaging (cerebral perfusion and markers of vascular brain damage).

Interventions and Duration

The intervention includes Montelukast (10, 20, or 40 mg) or placebo. The duration of the study is 1 year.

Sample Size and Population

Our target population includes subjects who are 50 years or older with MCI and early AD dementia. Our sample size is 30 for this trial.

TABLE 1. SCHEDULE OF PROCEDURES FOR THE DURATION OF THE STUDY

Phase:	SCREEN	BASELINE	FOLLOW-UP			
Number of visits	1-2 [@]	1-2				
Months	-1	0	1.5	3	6	12
Informed Consent	X					
Cognitive screening	X					
Screening labs	X*					
CSF for biomarker and molecular analysis		X**				X [^]
Weight/Height	X	X	X	X	X	X
Blood Pressure	X	X	X	X	X	X
Safety labs			X [#]	X [#]	X [#]	X [#]
Brain MRI		X				X
Vascular function measures (PWV/PWA)		X				X
Cognitive Battery		X			X	X
Functional battery (FAQ, IADL, SPPB)		X***				X
LTE₄ testing		X			X	X
Blood for biospecimen banking		X			X	X
Time (in minutes)	60-120	150-210	30	30	120-150	120-150

^{*}: Screening labs include: CBC, CMP (BUN, Cr, electrolytes, liver function test (LFT)), B12, TSH and PT/INR.

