1. STUDY OBJECTIVES

Our primary objective is to determine the safety and dose-response for and target engagement of the treatment with escalating doses of Montelukast in those with mild cognitive impairment (MCI) or early Alzheimer's disease (AD) dementia based on cognitive and functional evaluation.

Our secondary objectives are to assess the efficacy and estimate the effect size of up to 1-year treatment of Montelukast on biomarkers of neurodegeneration and neuro-inflammation, and vascular function; and to estimate the effect of Montelukast on cognitive function, functional measures, and vascular inflammatory and endothelial markers in MCI/early AD dementia.

[figure not shown]

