5. STUDY INTERVENTIONS

5.1. INTERVENTIONS, ADMINISTRATION, AND DURATION

Participants will be randomized to either Montelukast or placebo in a 1:1 fashion. All participants will be initiated on 10 mg. The dose will be increased in 2-week increments to 20 mg and 40 mg as long as participants report no intolerable symptoms or adverse events (e.g. jaundice, headache, GI symptoms, and neuropsychiatric changes), and liver enzymes checked at 6 weeks do not exceed 3X baseline levels. If participant had positive LFT change (3x increase), dose will be decreased to the prior level (20 mg or matched placebo) and LFT rechecked 2 weeks later. If LFT increases further, then dose will be decreased to 10 mg or matched placebo. If LFT are still increased 2 weeks after 10 mg or matched placebo, study medication will be discontinued. Treatment will be provided in similar capsules format to be taken orally 1-2 times a day. Investigators, study personnel and participants will be blinded for drug assignment. Participants will be treated for 1 year.

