6.7. LEUKOTRIENE INHIBITION ACTIVITY

Cysteinyl leukotrienes (LTE₄) and CysLT type-1 (CysLT1) receptor activity will be assessed via single blood or urine sampling at baseline, 6 and 12 month visits by a highly selective and sensitive Liquid Chromatography/Tandem Mass Spectrometry (LC/MS/MS) method described previously.^{78,79} We will use this as a measure to assess the degree of blockade of CysLT type-1 (CysLT1) receptor activity.

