6.10.2. ENROLLMENT, BASELINE, AND FOLLOW-UP

Once eligible, baseline evaluation will be completed. A clinical evaluation and LP will be done during the baseline visit, unless one was done earlier during screening. Biospecimens will be collected for inflammatory and endothelial markers. Once baseline data are collected, participants will be randomized into Montelukast or placebo. During the medication escalation period, participants will be monitored via follow-up phone calls every 2 weeks until max dose is achieved, or participant reports adverse events (see intervention for issues related to increased LFT). Participants will return for follow-up visits at 6 weeks post-randomization, and at 3, 6 and the final 12-month visit. Blood pressure, heart rate, weight, laboratory testing, adverse events (AE) or serious adverse events (SAE), pill count (to assess compliance), and use of non-study medications data will be collected for frequent monitoring. At least 1 follow-up phone call will also occur between 6 and 12 months. An optional modified phone/virtual visit will be completed as needed for any visit to collect data that can be reasonably collected by phone. This change is in response to the COVID-19 stay home orders. However, subjects will be given the option to continue doing portions of the visits virtually when normal business operations resume. All visits will have a +/- three-week window for subjects to reschedule as needed, except for the 6-week visit which will have a +/- one-week window. Study procedures and timeline are shown in **Table 1**.

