9.3. DATA ANALYSIS

Table 2 provides a list of main outcomes.

Table 2. Independent, main outcome and other variables to be used in the analyses	
Independent:	Group (Montelukast vs placebo)
Safety outcome:	GI symptoms (diarrhea, nausea, vomiting), anaphylaxis, elevated liver enzymes, PT/INR, behavioral changes, seizures, number of discontinuations from Montelukast, treatment-emergent AE/SAE, deaths
CSF outcomes:	CSF amyloid and tau, inflammatory proteins
Vascular outcomes:	PWV/PWA
Imaging outcomes:	Perfusion, hippocampal volume
Cognitive outcomes:	CDR, NIH Toolbox Cognition battery (NIHTB-CB)

Baseline characteristics including demographic, social and cognitive measures will be compared between the 2 groups to assess randomization fidelity. The list of the main variables is shown in Table 2. We will compare the change in our outcomes over the study period between the treatment and placebo arms using Mixed Models. For the dose response analysis, the dose vs cysLT-1 receptor activity will be plotted to explore the degree of cysteinyl leukotriene modulation at the various doses.

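### The dose-response part of the primary objective cannot be answered as designed: no LTE4 sample is scheduled at 10 or 20 mg, and no between-arm LTE4 analysis is named for target engagement

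*Combined protocol and SAP*

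**What the plan says.** The précis states that the primary objective is to "determine the safety, dose-response and target engagement of the treatment with escalating doses of Montelukast". Section 1 repeats this and ends the sentence with "based on cognitive and functional evaluation".

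On allocation and dose, section 5.1 says "Participants will be randomized to either Montelukast or placebo in a 1:1 fashion" and, for patients already started on 10 mg, "The dose will be increased in 2-week increments to 20 mg and 40 mg", provided symptoms and liver tests allow. There are no dose arms. Sections 5.1 and 7.4 provide for stepping the dose down after liver-test rises or adverse events.

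On measurement, section 6.7 makes LTE4 the gauge of receptor blockade and says it "will be assessed via single blood or urine sampling at baseline, 6 and 12 month visits". The LTE4 row of Table 1 agrees. During escalation, section 6.10.2 says "participants will be monitored via follow-up phone calls every 2 weeks until max dose is achieved". The first return visit is at 6 weeks, with safety labs but no LTE4 test and no banked blood. The same section says "All visits will have a +/- three-week window for subjects to reschedule as needed"; the 6-week visit has one week either way.

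On analysis, section 9.3 says that "the dose vs cysLT-1 receptor activity will be plotted to explore the degree of cysteinyl leukotriene modulation at the various doses". Changes in the trial's outcomes are to be compared between arms with mixed models. Table 2, the list of main outcomes, does not include LTE4, and its only independent variable is treatment group.

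**The concern.** A dose-response question needs observations at more than one active dose, obtained in a way that does not let the patient's response decide the dose. The plan has neither. On-schedule patients have left 10 mg and 20 mg long before the first on-treatment LTE4 sample. A patient who is still at, or back at, a lower dose at month 6 or 12 is there because escalation stopped or the dose was reduced for tolerability. Dose on the plot is then a marker for intolerance.

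The plot would therefore show placebo, a cluster at 40 mg, and perhaps a few selected points in between. It could not show whether 10 or 20 mg engages the target less than 40 mg. Yet it is the only analysis offered for a component of the primary objective, and a reader could take it as the answer. Meanwhile the question the randomised data can answer, whether montelukast as titrated changes LTE4 relative to placebo, has no named analysis.

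**Working it through.** **Inputs.** Two-week escalation steps from a 10 mg start (section 5.1). LTE4 at baseline and months 6 and 12 (section 6.7, Table 1). Visit windows of ±3 weeks, and ±1 week for the 6-week visit (section 6.10.2). 36 enrolled, 20% drop-out, 15 per arm (section 3). Month 6 is taken as week 26 and month 12 as week 52.

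**1. The plan's own figure.** 30 × 1.20 = 36, as stated. The point does not depend on it.

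**2. Dose at each visit, on schedule.** 10 mg in weeks 0–2, 20 mg in weeks 2–4, 40 mg from week 4.

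| Visit | Weeks, with window | Scheduled dose | LTE4? |
|---|---|---|---|
| 6 weeks | 5–7 | 40 mg | No |
| 3 months | 10–16 | 40 mg | No |
| 6 months | 23–29 | 40 mg | Yes |
| 12 months | 49–55 | 40 mg | Yes |

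Earliest on-treatment sample: 26 − 3 = week 23, which is 23 − 4 = 19 weeks after 40 mg starts. Section 5.1 could also be read as holding the 40 mg step until the 6-week liver check. The gap is then 23 − 6 = 17 weeks, and the conclusion is the same because no LTE4 is taken at the 6-week visit.

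**3. Sample count.** 15 active completers × 2 visits = 30 post-baseline samples. At 10 or 20 mg, on schedule: 0 of 30.

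**4. Unscheduled lower-dose patients.** The documents give no rate of failed escalation or step-down, so the share p is an assumption. The expected number among 15 is 15p; the chance of at least three is a binomial tail.

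| p | Expected below 40 mg | Chance of ≥3 |
|---|---|---|
| 5% | 0.75 | 4% |
| 10% | 1.5 | 18% |
| 20% | 3.0 | 60% |
| 30% | 4.5 | 87% |

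These few would be split across dose levels and all selected by tolerability.

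**5. Cognitive and functional measures.** If section 1 means dose-response to be judged on these, the gap remains. Table 1 places the cognitive battery at baseline and months 6 and 12, and the functional battery at baseline and month 12. Neither falls within escalation.

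**6. What is estimable.** For the montelukast-minus-placebo difference in LTE4 change at one visit, the 95% CI half-width in SD units of that change is t(0.975, 2n − 2) × √(2/n):

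- n = 12 per arm: 2.074 × 0.408 = 0.85
- n = 15 per arm: 2.048 × 0.365 = 0.75
- n = 18 per arm: 2.032 × 0.333 = 0.68

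Here 18 is every enrolled patient (36/2), 15 is the planned completers, and 12 is an assumed shortfall.

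**The case against.** The best reply is that this is a 30-patient Phase II trial and that section 9.3 promises only an exploratory plot, with no dose-level test, dose selection or decision rule. The phrase about various doses fits a plot by achieved dose, since the plan expects some step-downs. Each stepped-down patient has a baseline LTE4 value, and liver-test step-down applies to matched placebo as well. Tolerability is also followed by phone, against placebo, throughout escalation.

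Much of this is fair, but it does not close the gap. The plot is exploratory, whereas the objective it serves is to determine dose-response. A baseline value permits a within-patient change but does not remove the selection of who ends up at a lower dose. Placebo patients stepped down for liver tests need not resemble active patients stepped down for the same reason. Phone reports of tolerability are not the dose-response analysis that section 9.3 defines, and no by-dose safety analysis is specified. Placebo does supply a randomised 0 mg reference, but that informs montelukast as titrated, not 10 or 20 mg.

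Two further points stand. The closing phrase of the section 1 objective may only describe how the population is diagnosed; neither reading supplies the missing data. And the mixed-model sentence can be read to include LTE4, so the second part of this point is that the contrast is not explicitly specified, which is a matter of clarification.

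**Conclusion.** The concern holds. The stated primary objective claims something the design cannot deliver: under on-schedule titration, 0 of 30 active-arm post-baseline LTE4 samples are at 10 or 20 mg, and the first comes about 19 weeks (17 on the later reading) after 40 mg starts. Lower-dose points that arise off schedule are confounded with tolerability; how many there will be is unknown, and the 5–30% range above is assumed. The weight of the point rests on this mismatch.

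The missing LTE4 analysis is secondary. That contrast is randomised and estimable, to about ±0.75 SD at one visit with 15 per arm. This figure assumes a simple two-sample comparison with equal variances and no gain from baseline adjustment or from pooling visits.

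**What to change.** 1. In the précis and section 1, restate the primary objective as safety and target engagement at the dose reached. In section 9.3, label the plot as descriptive, by tolerated dose, and not an estimate of dose-response.
2. Add LTE4 to Table 2. State in section 9.3 that target engagement is analysed as the montelukast-minus-placebo difference in LTE4 change from baseline at months 6 and 12, in the planned mixed model, by assigned arm. In section 6.7, require the same sample type (blood or urine) for a given participant at every visit.

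Both are text changes and go to the IRB as a protocol modification (section 11.1). They add no visit, sample or dosing change. Fixing the sample type narrows a choice that section 6.7 now leaves open. The real cost is a narrower objective: the trial will not claim to compare 10, 20 and 40 mg.

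Optionally, LTE4 could be sampled in both arms at each escalation step, reporting the between-arm difference per step and stating that dose remains confounded with time on treatment. This is not cheap. Contacts during escalation are by phone, so the 10 and 20 mg samples would need extra visits or home collection with transport. On the two-week reading, the 40 mg sample could be taken at the existing 6-week visit. Assay costs rise in either case.

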7.2. METHODS FOR ASSESSING AND RECORDING SAFETY PARAMETERS

During the study, any problem reported by the participants will be recorded in the participant's research record (adverse event log), along with the start and stop dates. The problem may be related to the research participation or the drug used in the study (drug reaction). All adverse events will be rated on the following characteristics:

(i) Serious (YES/NO): A serious adverse event (SAE) is defined using the Code of Federal Regulations Title 21 definition as any event that results in any of the following outcomes: Death, a life-threatening adverse event, inpatient hospitalization or prolongation of existing hospitalization, a persistent or significant incapacity or substantial disruption of the ability to conduct normal life functions, or a congenital anomaly/birth defect.

(ii) Related to the research: All adverse events will be judged regarding their relationship to the research participation or the study drug as related, possibly related, probably related, unrelated, or unknown.

(iii) Severity: The severity of the AE will be rated on the following scale mild, moderate, severe, life-threatening, or death.

(iv) Anticipated or unanticipated: We use the Emory IRB definition of an unanticipated event as any event that is "unexpected, not described in the study documents, or if described before, it is now presenting with increased severity, duration, or frequency".

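### Safety is compared by arm over a year that is nominally about 92% at 40 mg, so an early signal during escalation would be diluted; add a descriptive table of adverse events by arm within scheduled windows

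*Combined protocol and SAP*

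**What the plan says.** Section 1 sets the primary objective as to "determine the safety and dose-response for and target engagement of the treatment with escalating doses of Montelukast". Section 5.1 describes the regimen: "Participants will be randomized to either Montelukast or placebo in a 1:1 fashion", everyone starts at 10 mg, and "The dose will be increased in 2-week increments to 20 mg and 40 mg", provided the participant tolerates the treatment. The same section refers to placebo matched to the 10 mg and 20 mg levels, and to blinding of participants and staff.

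In section 9.3, Table 2 lists the safety outcomes, which include adverse events, discontinuations and liver enzymes. It gives treatment group as the only independent variable. The comparison is stated in one sentence: "We will compare the change in our outcomes over the study period between the treatment and placebo arms using Mixed Models". The only analysis that uses dose is "the dose vs cysLT-1 receptor activity will be plotted to explore the degree of cysteinyl leukotriene modulation at the various doses". No section tabulates safety by dose step or by time window.

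Some of the data for such a table are already planned. Section 6.10.2 has phone calls every two weeks during escalation, and section 7.2 has each reported problem logged "along with the start and stop dates". The notes to Table 1 place the first on-treatment safety laboratory tests at 6 weeks.

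**The concern.** When a primary objective names safety under escalating doses, a reader will ask how the escalation itself was tolerated. The plan as written will not answer that. Symptoms that appear in the first weeks and then settle, or that lead to an early step-down, are pooled with some eleven months at the final dose. If the arms differ only early, the whole-year contrast can look close to null.

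The dose plot does not fill the gap. It concerns receptor activity. Its samples (section 6.7) are taken at baseline, 6 months and 12 months, when a participant on schedule is at 40 mg. Anyone at a lower dose by then either did not escalate or was stepped down.

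The design offers a better comparison than the plan uses. Both arms pass through the same schedule under blinding, so arms can be compared within early windows as randomised. If those windows are not fixed in advance, cut-points may later be chosen with the data in view.

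**Working it through.** **Inputs.** From the documents: 36 enrolled, 20% dropout and a target of 30 (section 3); 1:1 allocation, two-week increments and one year of treatment (section 5.1). Assumed: 18 per arm (36/2), a constant background event rate, and the per-window event rates used below. The documents give no event rate, and no power or precision figure for safety.

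**The plan's own figure.** 30 × (1 + 0.20) = 36, so the enrolment number is reproduced as an add-on of 20%. (A loss of 20% from 36 would leave 28.8, which does not affect this point.)

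**Share of the year at each dose, on schedule.**
- 10 mg: 2/52 = 3.8%
- 20 mg: 2/52 = 3.8%
- 40 mg: 48/52 = 92.3%

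**Dilution of an early signal.** If the rate ratio is RR in weeks 0-4 and 1 afterwards, and the background rate is constant, the whole-year rate ratio is (4 × RR + 48)/52.
- RR = 2: 56/52 = 1.08
- RR = 3: 60/52 = 1.15
- RR = 5: 68/52 = 1.31

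**What a two-week window can show.**
- Exposure per arm: 18 × 2/52 = 0.69 person-years.
- No events in 18: two-sided exact 95% upper limit 1 − 0.025^(1/18) = 18.5%. With 15 per arm: 1 − 0.025^(1/15) = 21.8%.
- Chance of at least one event among 18, 1 − (1 − p)^18: 60%, 85% and 98% for assumed p = 5%, 10% and 20%.
- Approximate 95% half-width of the difference between arms, 1.96 × √(2p(1 − p)/18): 14, 20 and 26 percentage points for the same p.

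**What each window estimates.**
- Weeks 0-2: all participants start at 10 mg, so arm against arm estimates the 10 mg step.
- Weeks 2-4: escalation depends on tolerability (section 5.1), so this window mixes participants at 20 mg with some who were not escalated. Those at 20 mg have already had two weeks at 10 mg. By assigned arm the contrast is still randomised, but it concerns the scheduled regimen.
- Weeks 4-6: nominally the first two weeks at 40 mg, up to the 6-week visit.
- Liver enzymes and other laboratory measures: none are scheduled in weeks 0-4. Even with the one-week visit window, the first sample falls nominally at 40 mg.

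**The case against.** The strongest reply is that the objective concerns a titrated regimen. On that reading, regimen against placebo over the year does answer the safety question, and 9.3 deliberately assigns dose-response to receptor activity. The wording allows this, so the missing table is not a contradiction in the plan. It remains true that the whole-year contrast says little about the escalation period, which is the distinctive part of an escalating regimen.

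A second reply is that the 9.3 sentence on change in outcomes does not clearly govern adverse event counts or deaths. That is fair: whole-year comparison by arm is the natural reading of 9.3 with Table 2, but no method for adverse events is spelled out. This makes a stated table more useful.

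A third is that the yield is low with 15 to 18 per arm. This stands, and it is why the table should be descriptive.

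Several stronger readings are tempting, and the documents do not support them:
- *The matched placebo gives every dose a clean randomised estimate, so the trial could show which step brings harm.* Only weeks 0-2 isolate a dose. Later windows are affected by conditional escalation and prior exposure, and a late effect of one step would be counted in the next.
- *Crude counts would make 40 mg look 24 times worse than 10 mg.* The ratio 48/2 = 24 is correct arithmetic for a constant rate, but no section proposes crude counts by dose.
- *The data cannot support the analysis because section 7.2 does not list dose at onset.* Windows by calendar week need only the onset date, which is recorded.

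**Conclusion.** The point holds as an inexpensive improvement. Safety under escalation is part of the primary objective, 9.3 plans no safety summary for the escalation period, and that period is 4 of 52 weeks (7.7%) on schedule. The loss is material for an effect confined to those weeks: even an assumed fivefold rate would appear as about 1.3 over the year. For an effect that persists at 40 mg the whole-year comparison loses little.

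The dilution figures rest on a constant background rate and on the nominal schedule being followed. The precision figures rest on 18 per arm. A reader should not infer that the 20 mg dose can be assessed on its own, or that laboratory safety at 10 mg or 20 mg can be recovered.

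**What to change.** Add to section 9.3 one prespecified descriptive table: number and percentage of participants with adverse event onset, by assigned arm, in weeks 0-2, 2-4, 4-6 and from week 6 to month 12. Give the risk difference with an exact 95% interval for each window, without a test. Keep every participant in the assigned arm whether or not the dose was escalated, and show the number still in follow-up in each window. Read the table across arms within a window only, because the last window is 46 weeks long (52 − 6) and the others two.

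State beneath the table:
- weeks 0-2 estimate the 10 mg step;
- weeks 2-4 estimate the scheduled regimen, 20 mg after 10 mg with non-escalated participants included;
- laboratory safety is not covered, because on-treatment tests start at 6 weeks;
- the estimates are imprecise.

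Event rates by dose level taken at onset are optional. If they are shown, label them non-randomised and confounded by step-downs for tolerability (sections 5.1 and 7.4) and by time since start.

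The cost is one paragraph in 9.3 and one table from dates already collected. No visit, sample or dosing rule changes. The downside is wide intervals that could be over-read, which the footnotes should prevent.
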